**Ora Calibra® Ocular Discomfort Scale**

For more information, contact the Office of the Vice President for Research and Economic Development at [contact] or [[contact]](mailto:[contact]).

© 2013 Pearson Education, Inc.

For more information, contact the Office of the Vice President for Research and Economic Development at [contact] or [[contact]](mailto:[contact]).

For more information, contact the Office of the Vice President for Research and Economic Development at [contact] or [[contact]](mailto:[contact]).

10

1

1

[figure not shown]
[figure not shown]
1

[figure not shown]
[figure not shown]
1

[figure not shown]
1

10

Page 10

© 2007 by the author

© 2013 Pearson Education, Inc.

www.english-test.net

\_\_\_\_\_

© 2013 Pearson Education, Inc. All Rights Reserved. May not be copied, scanned, or duplicated, in whole or in part. Due to electronic rights, some third party content may be suppressed from the eBook and/or eChapter(s). Editorial review has determined that any suppressed content does not materially affect the overall learning experience. Pearson Education, Inc. reserves the right to remove additional content at any time if subsequent rights restrictions require it.

© 2019 Pearson Education, Inc.

For more information, contact the Office of the Vice President for Research and Economic Development at [contact] or [[contact]](mailto:[contact]).

11. **What is the primary purpose of the *Journal of Clinical Endocrinology and Metabolism*?**

© 2019 Pearson Education, Inc.

For more information, contact the Office of the Vice President for Research and the Office of the Vice President for Student Affairs.

[www.ijerph.com](http://www.ijerph.com) | ISSN: 1660-4601 | DOI: 10.3390/ijerph16030750

—  
—

For more information, contact the Office of the Vice President for Research and the Office of the Vice President for Student Affairs.

For more information, contact the Office of the Vice President for Research and Economic Development at [contact] or [[contact]](mailto:[contact]).

© 2019 Pearson Education, Inc.

www.ijerpi.org | 100

Journal of Oral Rehabilitation 2006 33: 103–109

For more information, contact the Office of the Vice President for Research and Economic Development at [contact] or [[contact]](mailto:[contact]).

Digitized by [contact]

[REDACTED]

[REDACTED] [REDACTED]

[REDACTED] [REDACTED]

[REDACTED]

[REDACTED]

[REDACTED]

[REDACTED] [REDACTED]

[REDACTED] [REDACTED]

[REDACTED]

[REDACTED]

[REDACTED]

[REDACTED]

[REDACTED]

[REDACTED]

[REDACTED]

[REDACTED]

[REDACTED]

[REDACTED]

[REDACTED]

[REDACTED]

[REDACTED]

[REDACTED]

[REDACTED]

[REDACTED]

[REDACTED]

[REDACTED]

[REDACTED]

[REDACTED]

[REDACTED]

[REDACTED]

[REDACTED]

[REDACTED]

[REDACTED]

[REDACTED]

[REDACTED]

[REDACTED]

[REDACTED]

[REDACTED]

[REDACTED]

[REDACTED]

[REDACTED]

[REDACTED]

[REDACTED]

For more information, contact the Office of the Vice President for Research and the Office of the Vice President for Student Affairs.

For more information, contact the Office of the Vice President for Research and Economic Development at [contact] or [[contact]](mailto:[contact]).

Term	Percentage
Climate change	100
Global warming	95
Green energy	92
Carbon footprint	88
Sustainable development	90
Renewable energy	93
Emissions reduction	85
Green economy	91

[REDACTED]

[figure not shown]
[REDACTED]

[REDACTED]

[REDACTED]

[figure not shown]

### **Appendix 3: Amendment Summary of Changes**

Not applicable

DMP	Data Management Plan
eCRF	Electronic Case Report Form
ETDRS	Early Treatment of Diabetic Retinopathy Study
HIPAA	Health Information Portability and Accountability Act
ICH	International Conference on Harmonisation
IOP	Intraocular Pressure
ITT	Intent-to-Treat
LOCF	Last Observation Carried Forward
logMAR	Logarithm of the Minimum Angle of Resolution
MedDRA	Medical Dictionary for Regulatory Activities
NCS	Not clinically significant
OSDI	Ocular Surface Disease Index
PDF	Portable Document Format
PP	Per Protocol
PT	Preferred Term
RTF	Rich Text Format
SAAS	Software-as-a-Service
SAE	Serious Adverse Event
SANDE	Symptom Assessment in Dry Eye
SAP	Statistical Analysis Plan
SD	Standard Deviation
SDC	Statistics and Data Corporation, Incorporated
SOC	System Organ Class
SOP	Standard Operating Procedure
TEAE	Treatment-Emergent Adverse Event
TE-SAE	Serious Treatment-Emergent Adverse Event
VA	Visual Acuity
WHO DDE	World Health Organization Drug Dictionary Enhanced

1. Introduction

The purpose of this statistical analysis plan (SAP) is to describe the planned analyses and reporting for protocol ADX-102-DES-007, version 1.0 dated 27MAR2017.

This SAP is being written with due consideration of the recommendations outlined in the most recent International Conference on Harmonization (ICH) E9 Guideline entitled Guidance for Industry: Statistical Principles for Clinical Trials and the most recent ICH E3 Guideline, entitled Guidance for Industry: Structure and Content of Clinical Study Reports (CSR).

This SAP describes the data that will be analyzed and the subject characteristics, efficacy, and safety assessments that will be evaluated. This SAP provides details of the specific statistical methods that will be used. The statistical analysis methods presented in this document will supersede the statistical analysis methods described in the clinical protocol. If additional analyses are required to supplement the planned analyses described in this SAP they may be completed and will be identified in the CSR.

2. Study Objectives

The objective of this study is to evaluate the safety, tolerability and pharmacodynamic activity of ADX-102 Ophthalmic Solutions (0.5% and 0.1%) and ADX-102 Ophthalmic Lipid Solution (0.5%) in subjects with dry eye syndrome.

2.1 Study Variables

In this Phase 2a study there are no primary or secondary endpoints. Exploratory pharmacodynamic variables and safety variables follow.

2.3 Safety Variables

The safety variables include the following:

- Visual acuity (VA) (ETDRS [Early Treatment of Diabetic Retinopathy Study]);
- Slit-lamp biomicroscopy;
- Adverse event (AE) query;
- Undilated Fundoscopy;
- Intraocular Pressure (IOP).

2.4 Statistical Hypotheses

This is a Phase 2a study to assess the safety, tolerability and pharmacodynamic activity of ADX-102 Ophthalmic Solution in subjects with dry eye syndrome. There are no primary endpoints and no formal statistical hypotheses.

3. Study Design and Procedures

3.1 General Study Design

This is a Phase 2a, single-center, randomized, double-masked study designed to evaluate the safety, tolerability and pharmacodynamic activity of ADX-102 Ophthalmic Solution (0.5%), ADX-102 Ophthalmic Solution (0.1%), and ADX-102 Ophthalmic Lipid Solution (0.5%) in subjects with dry eye syndrome. Approximately 45 male and female subjects at least 18 years of age with a subject-reported history of dry eye in both eyes and meeting all other study eligibility criteria will be randomized to receive treatment ADX-102 Ophthalmic Solution (0.5%), ADX-102 Ophthalmic Solution (0.1%), or ADX-102 Ophthalmic Lipid Solution (0.5%) in a 1:1:1 ratio (approximately 15 subjects in each treatment group).

Study visits will be referred to in all tables and listings as the expected study day corresponding to the visit to enable reviewers to understand the assessment timing without referring to the protocol visit schedule. The following table shows the scheduled study visits, their planned study day (note that there is no Day 0 and that Day 1 corresponds to the day of randomization), and the acceptable visit window for each study visit:

Scheduled Visit	Planned Study Day	Visit Window
Visit 1	Day 1	N/A
Visit 2	Day 8	± 1 Day
Visit 3	Day 29	± 2 Days

3.2 Schedule of Visits and Assessments

The schedule of visits and assessments is provided below.

Procedure	Visit 1 Day 1	Visit 2 Day 8 ± 1	Visit 3 Day 29 ± 2
Informed Consent / HIPAA	X		
Medical / Medication History and Demographic	X		
Study Drug Collection		X	X
Medical / Medication History Update		X	X
Adverse Event Query		X	X
Urine Pregnancy Test	X ¹		X ¹
Ora Calibra® Ocular Discomfort Scale	X	X	X
Visual Acuity (ETDRS)	X	X	X
Review of Qualification Criteria	X		
Intraocular Pressure	X		X
Undilated Fundus Exam	X		X
Review Qualification Criteria	X		
Randomization	X		
Subject Self-instillation of Study Drug	X	X	
Study Drug Dispensation	X	X	
Adverse Event Query	X	X	X
Exit Subject from Study			X
X ¹ = For females of childbearing potential			

4. Study Treatments

4.1 Method of Assigning Subjects to Treatment Groups

Prior to initiation of study drug (at Visit 1), each subject who qualifies for entry will be assigned a screening number. All screening numbers will be assigned in strict numerical sequence at a site and no numbers will be skipped or omitted. If all inclusion and exclusion criteria are met at Visit 1, each qualifying subject will then be assigned a randomization number at the end of Visit 1.

A randomization schedule will be provided to the investigational site. The randomization schedule will use block randomization, such that there will be an approximate equal number of subjects assigned to each of the three treatment arms at the site. The site staff will dispense to the subject the study kit based on the subject's randomization number. The randomization number will be recorded on the subject's source document and electronic case report form (eCRF). A new kit will be dispensed at Visit 2 based on the subject's randomization. The Sponsor, Investigators, and study staff will be masked during the randomization process and throughout the study.

4.2 Masking and Unmasking

All subjects, investigators, and study personnel involved with the conduct of the study will be masked with regard to treatment assignments. When medically necessary, the investigator may need to determine what treatment arm has been assigned to a subject. When possible (i.e., in non-emergent situations), Ora and/or the study sponsor should be notified before unmasking study drug. The unmasked subject will be discontinued from the study.

5. Sample Size and Power Considerations

6. Data Preparation

Electronic Case Report Forms (eCRF) will be developed by Statistics and Data Corporation, Incorporated (SDC) following SDTM standards unless otherwise specified by Aldeyra. Data from source documents will be entered into the eCRF by site personnel. All users will complete role-based system and study-specific eCRF training prior to receiving access to the study database. User access will be granted based on a user's role in the study and will be controlled through individual login credentials including a unique User ID and password.

After data are entered into the clinical study database, electronic edit checks and data review will be performed. All data validation specifications and procedures are detailed in the Data Validation Manual as a separate document. When the database has been declared to be complete and accurate, the database will be locked. Any changes to the database after data have been locked can only be made with the approval of Aldeyra and Ora in consultation with SDC.

All analyses outlined in this document will be carried out after the following have occurred:

- All data management requirements are met according to SDC standard operating procedures (SOP), including data entry, performance of edit and validation checks, documentation and resolution of data queries, and database lock with written authorization provided by appropriate SDC, Aldeyra and Ora personnel;
- Protocol deviations have been identified and status defined (major/minor deviations);
- Analysis populations have been determined; and
- Randomized treatment codes have been unmasked.

7. Analysis Populations

Analysis populations include the intent-to-treat (ITT) population, the per-protocol (PP) population, and the Safety population. The statistical analysis of safety data will be performed on the Safety population. The analysis of baseline and exploratory efficacy data will be performed on the ITT population, and may be performed on the PP population as sensitivity analyses if it differs substantially from the ITT population.

7.1 Intent-to-Treat

The ITT population includes all randomized subjects. Subjects in the ITT population will be analyzed as randomized.

7.2 Per Protocol

The PP population includes subjects in the ITT population who do not have significant protocol deviations and who complete the study. Protocol deviations will be assessed prior to database lock and unmasking. Subjects in the PP population will be analyzed as treated.

7.3 Safety

The Safety population includes all randomized subjects who have received at least one dose of the investigational product. Subjects in the Safety population will be analyzed as treated.

8. General Statistical Considerations

8.1 Unit of Analysis

Safety endpoints will be analyzed for both eyes. For efficacy endpoints, the unit of analysis will be the study eye, or the “worst eye,” as defined by the following:

Worst Eye: Eyes are eligible for analysis if they meet all of the inclusion criteria. In the case that both eyes are eligible for analysis, the worst eye will be the eye with worst (higher) total corneal fluorescein staining, based on the sum of the inferior, superior, and central regions, at Visit 1. If the total corneal staining is the same in both eyes then the eye with the worst (higher) Ora Calibra® Ocular Discomfort Scale score at Visit 1 will be the worst eye. If the total corneal staining and ocular discomfort scores are the same for both eyes, then the right eye will be selected as the worst eye.

8.2 Missing or Inconclusive Data Handling

[REDACTED]

8.3 Definition of Baseline

[REDACTED]

8.4 Data Analysis Conventions

[REDACTED]

[REDACTED]

Summaries for continuous and ordinal variables will include the number of observations (n), arithmetic mean, standard deviation (SD), median, minimum, and maximum. Minima and maxima will be reported with the same precision as the raw values; means and medians will be presented to one additional decimal place than reported in the raw values. Standard deviations will be presented to two additional decimal places than reported in the raw values. Summaries for discrete variables will include frequency counts and percentages. All percentages will be rounded to one decimal place (i.e., XX.X%).

All statistical tests will be two-sided with a significance level of 0.05 ($\alpha = 0.05$) unless otherwise specified. Confidence intervals (CI) for differences between treatment groups will be two-sided at 80% and 95% confidence levels where appropriate. All p-values will be rounded to four decimal places; p-values less than 0.0001 will be presented as “<0.0001”; p-values greater than 0.9999 will be presented as “>0.9999”.

8.5 Adjustments for Multiplicity

9. Disposition of Subjects

Subject disposition will be presented in terms of the numbers and percentages of subjects who were randomized, completed the study, and discontinued from the study. Subjects who are not discontinued from the study will be considered study completers. Disposition will be summarized by treatment group and for all subjects.

The number of subjects in each of the analysis populations (ITT, PP and Safety) will be displayed by treatment and percentages will be calculated using randomized subjects as the denominator.

The number and percentage of subjects prematurely discontinued from the study and the reasons for study discontinuation will be summarized by treatment group for all randomized subjects. The reasons for study discontinuation that will be summarized include: (AE, protocol violation, administrative reasons (e.g., inability to continue, lost to follow up), sponsor termination of study, subject choice, and other. A subject listing will be provided that includes the date of and reason for premature study discontinuation.

The number and percentage of subjects with major protocol deviations will be summarized by treatment group for all randomized subjects. The protocol deviations that will be summarized include: Informed Consent, Inclusion / Exclusion and Randomization, Test Article / Study Drug Instillation and Assignment at Site, Improper Protocol Procedures at Site, Site's Failure to Report SAE / AE, Visit Out of Window, Subject's Non-compliance with Test Article, Subject's Use of Prohibited Concomitant Medication, Subject's Failure to Follow Instructions, and Other. A subject listing will be provided that includes the date and description of each deviation.

In addition, subject listings will be provided that include treatment, whether inclusion and exclusion criteria were met, and inclusion in the ITT, Safety, and PP populations.

10. Demographic and Pretreatment Variables

10.1 Demographic Variables

The demographic variables collected in this study include age, sex, race, ethnicity and iris color. Demographic variables will be summarized, overall and by treatment group, for the ITT and Safety populations, separately.

Age (years) will be summarized using continuous descriptive statistics. Age will also be categorized as follows: <65 years and ≥65 years. Age will be reported in years and calculated using the following formula:

$$\text{Age} = (\text{informed consent date} - \text{date of birth}) / 365.25 \text{ truncated as an integer}$$

The number and percentage of subjects will be presented for age category, sex, race, ethnicity and iris color.

A subject listing that includes all demographic variables for the ITT population will be provided.

10.2 Pretreatment Variables

Baseline disease characteristics will be summarized by treatment group using continuous descriptive statistics for Ora Calibra® Ocular Discomfort Scale, corneal sum and total fluorescein staining, conjunctival sum and total lissamine green staining, TFBUT, SANDE questionnaire, VA, tear osmolarity, unanesthetized Schirmer's test, OSDI®, and IOP.

11. Medical History and Concomitant Medications

11.1 Medical History

Medical history will be coded using MedDRA Version 20.0.

Non-ocular medical history will be summarized using discrete summary statistics and presented by treatment group at the subject and event level by System Organ Class (SOC) and Preferred Term (PT) using the ITT population. Ocular medical history will be similarly summarized at the subject and event level. If a subject reports the same PT multiple times within the same SOC, that PT will only be reported once within that SOC. As with the PT, if a subject reports multiple conditions within the same SOC, that SOC will only be reported once.

Listings of medical history will be generated separately for ocular and non-ocular data.

11.2 Concomitant Medications

Concomitant medications will be coded using WHO Drug Dictionary March 2017 and summarized to the therapeutic drug class (Anatomical Therapeutic Chemical (ATC) 4 classification) and preferred name. ATC classifications are applied based on the route and indication by which the drug was taken. If no route or indication is reported/available, the first ATC in alphabetic order will be applied. In cases where the trade name of the drug is reported, SDC will code to the trade name. If this is not available in the dictionary, then the generic name of the drug will be selected. If neither the trade nor generic names are available, SDC will code the medication to the appropriate general category based on the indication and route. If a multi-ingredient/combination drug trade name is not available in the current dictionary, SDC will code to the generic combination if available. If this is not available, SDC will code to the General category based on the reported Indication. Additional coding guidelines are specified in the Data Management Plan (DMP). Terms that remain uncoded after the coding guidelines have been followed will be forwarded to the Medical Monitor along with a list of potential coding links available in the dictionary. The Medical Monitor will either select one of the terms from the potential coding links or specify an alternate term that is available in the dictionary.

Concomitant medications are defined as those medications listed as having been taken 1) within 30 days prior to initiation of study drug administration and continuing for any period of time following the first administration of study drug or 2) at any time following the first administration of study drug.

Concomitant medications will be summarized using the ITT population. Ocular and non-ocular medications will be summarized separately. Medications will be tabulated for each treatment group using frequencies and percentages. Subjects may have more than 1 medication per ATC text. At each level of subject summarization, a subject will be counted once if he/she reports 1 or more medications. Percentages will be based on the number of subjects in each treatment group. Listings of concomitant medications will be generated separately for ocular and non-ocular data.

12. Dosing Compliance and Treatment Exposure

12.1 Dosing Compliance

[REDACTED]

[REDACTED]

[REDACTED]

[REDACTED]

[REDACTED]

[REDACTED]

[REDACTED]

A large black rectangular redaction box covers the majority of the page content. Above and to the left of this main box, there are several smaller black rectangular redaction boxes of varying sizes, creating a visual hierarchy. The redaction boxes are solid black and do not contain any text or other markings.

12.2 Treatment Exposure

Extent of treatment exposure for completed or discontinued subjects will be calculated in days using the following:

Extent of Exposure (days) = Date of completion/discontinuation – date of Visit 1 (Day 1)

Extent of treatment exposure for subjects who were lost to follow-up will be calculated in days using the following:

Extent of Exposure (days) = Date of last recorded visit – date of Visit 1 (Day 1) + 1

Extent of treatment exposure (days) for each subject exposed to study drug will be summarized with continuous descriptive statistics for each treatment group, using the Safety population. A subject listing of treatment exposure will also be produced.

13. Efficacy Analyses

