## SYNOPSIS

Protocol Title:	A Single-Center, Phase 2a, Randomized, Double-Masked, Clinical Study to Assess the Safety, Tolerability, and Pharmacodynamic Activity of ADX-102 Ophthalmic Solution in Subjects with Dry Eye Syndrome
Protocol Number:	ADX-102-DES-007
Study Drug:	1) ADX-102 Ophthalmic Solution (0.5%) 2) ADX-102 Ophthalmic Solution (0.1%) 3) ADX-102 Ophthalmic Lipid Solution (0.5%)
Study Phase:	2a
Study Objective:	The objective of this study is to evaluate the safety, tolerability, and pharmacodynamic activity of ADX-102 Ophthalmic Solutions and ADX-102 Ophthalmic Lipid Solution in subjects with dry eye syndrome.
Overall Study Design	
Structure:	Single-center, double-masked, randomized study
Duration:	An individual subject's participation is estimated to be approximately 4 weeks (28 days).
Dosage/Dose Regimen:	Subjects eligible to be randomized will receive one of the following treatments to be administered bilaterally four times daily (QID) for 28 days (from Visit 1 to Visit 3). 1) ADX-102 Ophthalmic Solution (0.5%) 2) ADX-102 Ophthalmic Solution (0.1%) 3) ADX-102 Ophthalmic Lipid Solution (0.5%)
Summary of Visit Schedule:	3 visits over the course of approximately 4 weeks 

• Visit 1 = Day 1, Screening and Enrollment

• Visit 2 = Day 8 ± 1, 1-Week Follow-Up

• Visit 3 = Day 29 ± 2, 4-Week Follow-Up

Measures Taken to Reduce Bias:	This is a randomized treatment assignment, double-masked study.
Study Population Characteristics	
Number of Subjects:	Approximately 60 subjects will be screened to enroll 45 subjects (15 per treatment arm).
Condition/Disease:	Dry Eye Syndrome (DES)

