### **5.5 Withdrawal Criteria (if applicable)**

If at any time during the study the investigator determines that a subject's safety has been compromised, the subject may be withdrawn from the study.

Subjects may withdraw consent from the study at any time.

Sponsor and/or investigator may discontinue any subject for non-compliance or any valid medical reason (see [Section 8.6.2](#)).

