### 7.1.2 Dispensation Schedule

- At the end of Visit 1, qualified subjects will be randomized and the first dose of study drug will be administered in office. A supply of ADX-102 Ophthalmic Solution (0.5%), ADX-102 Ophthalmic Solution (0.1%), or ADX-102 Ophthalmic Lipid Solution (0.5%) will be dispensed for dosing QID.
- At the end of Visit 2, the unused vials from their Visit 1 kit will be re-dispensed to subjects, and a second kit for dosing through Visit 3 will also be dispensed.
- At Visits 2 and 3, remaining/used study drug will be collected from subjects for drug accountability.
- Subjects will be instructed to not use study drug on the day of visits (Visit 2 and 3) prior to the visit.

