## 8.6 Subject Disposition

### 8.6.1 Completed Subjects

A completed subject is one who has not been discontinued from the study.

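### SAP 12.2 measures exposure to the end of study participation, not to the last dose, so a subject who stops the drops early but attends Visit 3 is reported with full exposure

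*SAP*

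**What the plan says.** SAP 12.2 gives two formulas. The first is introduced with "Extent of treatment exposure for completed or discontinued subjects will be calculated in days using the following", and it is "Extent of Exposure (days) = Date of completion/discontinuation – date of Visit 1 (Day 1"). For those lost to follow-up, it is "Extent of Exposure (days) = Date of last recorded visit – date of Visit 1 (Day 1) + 1". The result is summarised by arm in the Safety population and listed by subject.

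The end date in the first formula depends on who counts as completed, and both documents settle that by study status alone. Protocol 8.6.1 says "A completed subject is one who has not been discontinued from the study", and SAP section 9 says "Subjects who are not discontinued from the study will be considered study completers". Neither asks whether the subject was still using the drops.

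Discontinuing a subject who is not dosing is optional. Protocol 5.5 says "Sponsor and/or investigator may discontinue any subject for non-compliance or any valid medical reason".

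The Protocol synopsis plans treatment to be "administered bilaterally four times daily (QID) for 28 days (from Visit 1 to Visit 3"). Protocol 7.1.2 places the start of dosing at Visit 1, where "qualified subjects will be randomized and the first dose of study drug will be administered in office".

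**The concern.** The quantity is labelled treatment exposure, but no dosing date enters it at the end. A subject can stop the drops, stay in the study and attend Visit 3. Under the definitions above that subject is a completer, and the formula runs to Visit 3. A subject who stops some days before being formally discontinued is overstated in the same way, by the length of the gap.

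The trial's stated objective is the safety and tolerability of two concentrations and a lipid formulation. Early stopping that differs between arms is something a reader would expect an exposure table to show. As defined, the table can show a difference only if the early stopper also leaves the study. At stake is the accuracy of one descriptive table and one listing, and how they are read beside the safety tables.

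**Working it through.** **Inputs**
- First dose: Day 1, in the clinic at Visit 1 (Protocol 7.1.2).
- Visit 3: Day 29 ± 2, with no Day 0 (SAP 3.1).
- Planned dosing: 28 days (Protocol synopsis).
- Arm size: about 15 (SAP 3.1).
- Day of last dose for an early stopper, and number of such subjects: not in the documents, so assumed and varied below.

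**The plan's own figure.** For a completer seen on Day 29, the SAP formula gives 29 − 1 = 28 days, which matches the planned 28 days. Across the visit window it gives 27 − 1 = 26 to 31 − 1 = 30 days. For a subject who doses throughout and takes the last dose on Day 28, a dosing-based count (last dose day − first dose day + 1) is 28 − 1 + 1 = 28. The two measures agree when nobody stops early.

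**One subject who stops early and attends Visit 3 on Day 29**

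| Last dose | SAP 12.2 (29 − 1) | Last − first + 1 | Overstated by |
|---|---|---|---|
| Day 1 | 28 | 1 | 27 |
| Day 5 | 28 | 5 | 23 |
| Day 8 | 28 | 8 | 20 |
| Day 15 | 28 | 15 | 13 |
| Day 22 | 28 | 22 | 6 |

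The SAP column does not change with the last dose.

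**Arm of 15, all others at 28 days (assumed).** The reported mean is 28.0 in every row.
- One stops on Day 22: (14 × 28 + 22)/15 = 414/15 = 27.6, a shortfall of 0.4/28 = 1.4%.
- One stops on Day 8: (14 × 28 + 8)/15 = 400/15 = 26.7.
- One stops on Day 5: (14 × 28 + 5)/15 = 397/15 = 26.5.
- Three stop on Day 8: (12 × 28 + 3 × 8)/15 = 360/15 = 24.0.
- Three stop on Day 5: (12 × 28 + 3 × 5)/15 = 351/15 = 23.4, a shortfall of 4.6/28 = 16%.

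In all of these the median stays at 28. The minimum changes most: 28 as reported, against 5, 8 or 22 when counted to the last dose.

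**Side check.** The two SAP formulas also differ by a day. With the same end date of Day 8, a discontinued subject gets 8 − 1 = 7 days and one lost to follow-up gets 8 − 1 + 1 = 8. This is separate from the end-date problem, but a single formula would remove both.

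**The case against.** **Nothing else in the visible plan depends on this number.** A reader might infer that exposure is the denominator for the adverse event results, so that these are biased too. The documents do not support that. Protocol 10.4.7 and SAP 15.1 use counts and percentages of subjects, and no person-time rate appears. This objection stands, and it confines the point to 12.2.

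**Early stopping may show elsewhere.** A reader might infer that the tolerability signal is lost. That does not follow either. Protocol 8.5 has vials collected at Visits 2 and 3 to assess compliance. SAP 12.1, on dosing compliance, is blacked out in the public version and may report under-dosing. SAP section 9 tabulates, by arm, reasons for discontinuation and major deviations, including non-compliance with study drug. An adverse event that led a subject to stop should itself be recorded, with the action taken (Protocol 9.1). This also stands, but none of these sources enters the 12.2 formula, and a vial count need not show when dosing ended.

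**The scenario is assumed.** A subject who stops because of an adverse event can be discontinued (Protocol 8.6.2), which could bring the end date close to the stop date. Nothing in the documents suggests that three of 15 would stop by Day 5 and still complete, so the 16% is an illustration, not a forecast. Because discontinuation is optional, the gap remains possible.

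**Discontinuation in 12.2 might mean stopping treatment.** The visible text speaks only of discontinuation from the study (Protocol 8.6.2, SAP section 9), and no separate off-treatment status appears. Even on that reading, someone who stops the drops without being formally discontinued is still a completer.

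**Conclusion.** The point holds, as a minor one. SAP 12.2 reports time in study under the name of treatment exposure. For a subject who attends Visit 3 on Day 29 the figure is 28 days whatever the last-dose day, an overstatement of 27 days at one end (last dose Day 1) and 6 at the other (Day 22). These per-subject figures follow from the formula and the definition of a completer; only the stop day is assumed.

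The arm-level size rests on an unknown number of early stoppers and on everyone else having 28 days. Over the cases shown, the mean counted to the last dose runs from 27.6 to 23.4 days against 28.0 reported. If nobody stops early, the error is nil.

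The conclusion reaches the 12.2 summary and listing and no further. It is not a finding that adverse event results are distorted, or that the plan as a whole cannot detect poor tolerability.

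**What to change.** In SAP 12.2, define extent of exposure for all subjects as the date of last study-drug dose minus the date of first dose, plus 1. Record the last-dose date at Visit 3 or early termination if the eCRF, which is not among the documents, does not already do so. Use the last recorded visit only where that date cannot be obtained, and flag those subjects in the listing. Keep the present calculation as a separate line labelled time in study.

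The cost is at most one date field and a changed formula, and the exposure figures may look slightly less favourable. A first-to-last-dose span still overstates use when dosing is intermittent, so it complements a vial-based compliance measure and does not replace it.
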